11.0 Treatment Evaluation Using RECIST Guideline

NOTE: This study uses protocol RECIST v1.1 template dated 2/16/2011. See the footnote for the table regarding measurable disease in Section 11.44, as it pertains to data collection and analysis.

Response and progression will be evaluated in this study using the new international criteria proposed by the revised Response Evaluation Criteria in Solid Tumors (RECIST) guidelines (version 1.1) (Eisenhauer et al., 2009). Changes in the largest diameter (unidimensional measurement) of the tumor lesions and the short axis measurements in the case of lymph nodes are used in the RECIST guideline.

11.1 Schedule of Evaluations: For the purposes of this study, patients should be reevaluated every 8 weeks.

11.2 Definitions of Measurable and Non-Measurable Disease**11.21 Measurable Disease**

- 11.211 A non-nodal lesion is considered measurable if its longest diameter can be accurately measured as ≥ 2.0 cm with chest x-ray, or as ≥ 1.0 cm with CT scan, CT component of a CT, or MRI.
- 11.212 A superficial non-nodal lesion is measurable if its longest diameter is ≥ 1.0 cm in diameter as assessed using calipers (e.g. skin nodules) or imaging. In the case of skin lesions, documentation by color photography, including a ruler to estimate the size of the lesion, is recommended.
- 11.213 A malignant lymph node is considered measurable if its short axis is ≥ 1.5 cm when assessed by CT scan (CT scan slice thickness recommended to be no greater than 5 mm).

11.22 Non-Measurable Disease

- 11.221 All other lesions (or sites of disease) are considered non-measurable disease, including pathological nodes (those with a short axis ≥ 1.0 to < 1.5 cm). Bone lesions, leptomeningeal disease, ascites, pleural/pericardial effusions, lymphangitis cutis/pulmonis, inflammatory breast disease, and abdominal masses (not followed by CT or MRI), are considered as non-measurable as well.

Note: 'Cystic lesions' thought to represent cystic metastases can be considered as measurable lesions, if they meet the definition of measurability described above. However, if non-cystic lesions are present in the same patient, these are preferred for selection as target lesions. In addition, lymph nodes that have a short axis < 1.0 cm are considered non-pathological (i.e., normal) and should not be recorded or followed.

11.3 Guidelines for Evaluation of Measurable Disease

11.31 Measurement Methods:

- All measurements should be recorded in metric notation (i.e., decimal fractions of centimeters) using a ruler or calipers.
- The same method of assessment and the same technique must be used to characterize each identified and reported lesion at baseline and during follow-up. For patients having only lesions measuring at least 1 cm to less than 2 cm must use CT imaging for both pre- and post-treatment tumor assessments.
- Imaging-based evaluation is preferred to evaluation by clinical examination when both methods have been used at the same evaluation to assess the antitumor effect of a treatment.

11.32 Acceptable Modalities for Measurable Disease:

- Conventional CT and MRI: This guideline has defined measurability of lesions on CT scan based on the assumption that CT slice thickness is 5 mm or less. If CT scans have slice thickness greater than 5 mm, the minimum size for a measurable lesion should be twice the slice thickness.
- As with CT, if an MRI is performed, the technical specifications of the scanning sequences used should be optimized for the evaluation of the type and site of disease. The lesions should be measured on the same pulse sequence. Ideally, the same type of scanner should be used and the image acquisition protocol should be followed as closely as possible to prior scans. Body scans should be performed with breath-hold scanning techniques, if possible.

11.33 Measurement at Follow-up Evaluation:

- In the case of stable disease (SD), follow-up measurements must have met the SD criteria at least once after study entry at a minimum interval of 8 weeks (see Section 11.44).
- The cytological confirmation of the neoplastic origin of any effusion that appears or worsens during treatment when the measurable tumor has met criteria for response or stable disease is mandatory to differentiate between response or stable disease (an effusion may be a side effect of the treatment) and progressive disease.
- Cytologic and histologic techniques can be used to differentiate between PR and CR in rare cases (e.g., residual lesions in tumor types such as germ cell tumors, where known residual benign tumors can remain.)

11.4 Measurement of Effect

11.41 Target Lesions & Target Lymph Nodes

- Measurable lesions (as defined in Section 11.21) up to a maximum of 5 lesions representative of all involved organs, should be identified as “Target Lesions” and recorded and measured at baseline. These lesions can be non-nodal or nodal (as defined in 11.21), where no more than 2 lesions are from the same organ and no more than 2 malignant nodal lesions are selected.

Note: If fewer than 5 target lesions and target lymph nodes are identified (as there often will be), there is no reason to perform additional studies beyond those specified in the protocol to discover new lesions.

- Target lesions and target lymph nodes should be selected on the basis of their size, be representative of all involved sites of disease, but in addition should be those that lend themselves to reproducible repeated measurements. It may be the case that, on occasion, the largest lesion (or malignant lymph node) does not lend itself to reproducible measurements in which circumstance the next largest lesion (or malignant lymph node) which can be measured reproducibly should be selected.
- Baseline Sum of Dimensions (BSD): A sum of the longest diameter for all target lesions plus the sum of the short axis of all the target lymph nodes will be calculated and reported as the baseline sum of dimensions (BSD). The BSD will be used as reference to further characterize any objective tumor response in the measurable dimension of the disease.
- Post-Baseline Sum of the Dimensions (PBSD): A sum of the longest diameter for all target lesions plus the sum of the short axis of all the target lymph nodes will be calculated and reported as the post-baseline sum of dimensions (PBSD). If the radiologist is able to provide an actual measure for the target lesion (or target lymph node), that should be recorded, even if it is below 0.5 cm. If the target lesion (or target lymph node) is believed to be present and is faintly seen but too small to measure, a default value of 0.5 cm should be assigned. If it is the opinion of the radiologist that the target lesion or target lymph node has likely disappeared, the measurement should be recorded as 0 cm.
- The minimum sum of the dimensions (MSD) is the minimum of the BSD and the PBSD.

11.42 Non-Target Lesions & Non-Target Lymph Nodes

Non-measurable sites of disease (Section 11.22) are classified as non-target lesions or non-target lymph nodes and should also be recorded at baseline. These lesions and lymph nodes should be followed in accord with 11.433.

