11.43 Response Criteria

- 11.431 All target lesions and target lymph nodes followed by CT/MRI must be measured on re-evaluation at evaluation times specified in Section 11.1. Specifically, a change in objective status to either a PR or CR cannot be done without re-measuring target lesions and target lymph nodes.

Note: Non-target lesions and non-target lymph nodes should be evaluated at each assessment, especially in the case of first response or confirmation of response. In selected circumstances, certain non-target organs may be evaluated less frequently. For example, bone scans may need to be repeated only when complete response is identified in target disease or when progression in bone is suspected.

11.432 Evaluation of Target Lesions

- Complete Response (CR): All of the following must be true:
 - a. Disappearance of all target lesions.
 - b. Each target lymph node must have reduction in short axis to <1.0 cm.
- Partial Response (PR): At least a 30% decrease in PBSD (sum of the longest diameter for all target lesions plus the sum of the short axis of all the target lymph nodes at current evaluation) taking as reference the BSD (*see* Section 11.41).
- Progression (PD): At least one of the following must be true:
 - a. At least one new malignant lesion, which also includes any lymph node that was normal at baseline (< 1.0 cm short axis) and increased to ≥ 1.0 cm short axis during follow-up.
 - b. At least a 20% increase in PBSD (sum of the longest diameter for all target lesions plus the sum of the short axis of all the target lymph nodes at current evaluation) taking as reference the MSD (Section 11.41). In addition, the PBSD must also demonstrate an absolute increase of at least 0.5 cm from the MSD.
- Stable Disease (SD): Neither sufficient shrinkage to qualify for PR, nor sufficient increase to qualify for PD taking as reference the MSD.

11.433 Evaluation of Non-Target Lesions & Non-target Lymph Nodes

- Complete Response (CR): All of the following must be true:
 - a. Disappearance of all non-target lesions.
 - b. Each non-target lymph node must have a reduction in short axis to <1.0 cm.
- Non-CR/Non-PD: Persistence of one or more non-target lesions or non-target lymph nodes.
- Progression (PD): At least one of the following must be true:
 - a. At least one new malignant lesion, which also includes any lymph node that was normal at baseline (< 1.0 cm short axis) and increased to ≥ 1.0 cm short axis during follow-up.

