 - b. Unequivocal progression of existing non-target lesions and non-target lymph nodes. (NOTE: Unequivocal progression should not normally trump target lesion and target lymph node status. It must be representative of overall disease status change.)

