11.44 Overall Objective Status

The overall objective status for an evaluation is determined by combining the patient's status on target lesions, target lymph nodes, non-target lesions, non-target lymph nodes, and new disease as defined in the following tables:

For Patients with Measurable Disease

Target Lesions & Target Lymph Nodes	Non-Target Lesions & Non-Target Lymph Nodes	New Sites of Disease	Overall Objective Status
CR	CR	No	CR
CR	Non-CR/Non-PD	No	PR
PR	CR Non-CR/Non-PD	No	PR
CR/PR	Not All Evaluated*	No	PR**
SD	CR Non-CR/Non-PD Not All Evaluated*	No	SD
Not all Evaluated	CR Non-CR/Non-PD Not All Evaluated*	No	Not Evaluated (NE)
PD	Unequivocal PD CR Non-CR/Non-PD Not All Evaluated*	Yes or No	PD
CR/PR/SD/PD/Not all Evaluated	Unequivocal PD	Yes or No	PD
CR/PR/SD/PD/Not all Evaluated	CR Non-CR/Non-PD Not All Evaluated*	Yes	PD

*See Section 11.431

** NOTE: This study uses the protocol RECIST v1.1 template dated 2/16/2011. For data collection and analysis purposes the objective status changed from SD to PR in the ACCRU protocol RECIST v1.1 template as of 2/16/2011 and to match RECIST v1.1 requirements.

For Patients with Non-Measurable Disease Only:

Non-Target Lesions & Non-Target Lymph Nodes	New Sites of Disease	Overall Objective Status
CR	No	CR
Non-CR/Non-PD	No	Non-CR/Non-PD
Not All Evaluated*	No	Not Evaluated (NE)
Unequivocal PD	Yes or No	PD
Any	Yes	PD

*See Section 11.431

- 11.45 Symptomatic Deterioration: Patients with global deterioration of health status requiring discontinuation of treatment without objective evidence of disease progression at that time, and not either related to study treatment or other medical conditions, should be reported as PD due to “symptomatic deterioration.” Every effort should be made to document the objective progression even after discontinuation of treatment due to symptomatic deterioration. A patient is classified as having PD due to “symptomatic deterioration” if any of the following occur that are not either related to study treatment or other medical conditions:
- Weight loss >10% of body weight.
 - Worsening of tumor-related symptoms.
 - Decline in performance status of >1 level on ECOG scale.

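### Section 11.42 leaves measurable lesions beyond the target limits in no class, so progression confined to them can go unscored at the scan that decides the primary endpoint

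*Combined protocol and SAP*

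**What the plan says.** Section 11.41 takes measurable lesions, "up to a maximum of 5 lesions representative of all involved organs, should be identified as" target lesions, with the further limit that "no more than 2 lesions are from the same organ and no more than 2 malignant nodal lesions are selected".

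Section 11.42 defines the other baseline class: "Non-measurable sites of disease (Section 11.22) are classified as non-target lesions or non-target lymph nodes and should also be recorded at baseline". The section it refers to, 11.22, is the complement of the measurability definition in 11.21: "All other lesions (or sites of disease) are considered non-measurable disease, including pathological nodes" whose short axis is below the measurable threshold.

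The progression rules then work on these classes. For target disease (11.432) the size criterion is "At least a 20% increase in PBSD (sum of the longest diameter for all target lesions plus the sum of the short axis" of the target nodes, measured against the minimum sum, with an absolute increase of at least 0.5 cm. For non-target disease (11.433) it is "Unequivocal progression of existing non-target lesions and non-target lymph nodes", with a note that such progression should not normally override target status and must reflect a change in overall disease. A new malignant lesion counts under either heading. Overall status in 11.44 is "determined by combining the patient's status on target lesions, target lymph nodes, non-target lesions, non-target lymph nodes, and new disease".

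Section 16.21 counts a patient as a success if alive and progression free at the first disease evaluation scan, with status assessed by RECIST v1.1.

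**The concern.** A lesion can meet 11.21 and still not be selected as a target because a limit in 11.41 has been reached. It is then not a target lesion. It is not non-measurable either, so 11.42 does not make it non-target. Being present at baseline, it is not new disease. The text has no fourth class.

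The primary endpoint depends on whether progression is called at one scan. If disease grows only in unclassified lesions, the written rules return stable disease or better and the patient counts as a success. An error of this kind runs one way: progressions are missed, never added. The same status feeds PFS and the end date of duration of response. Entry requires metastatic, measurable disease (3.12, 3.14), and the laboratory criteria in 3.17 provide for liver involvement, so more than two measurable lesions in one organ is a foreseeable situation.

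**Working it through.** **Step 1: trace one lesion through Section 11.** Take a hypothetical patient with four measurable liver metastases and no other disease. Two are chosen as targets and stay stable. The other two grow from 2.0 to 4.0 cm by the first scan.

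| Section | Question | Answer for the two surplus lesions |
|---|---|---|
| 11.21 | Measurable? | Yes, at least 1.0 cm on CT |
| 11.41 | Target? | No, two per organ already reached |
| 11.22 / 11.42 | Non-measurable, hence non-target? | No, they meet 11.21 |
| 11.432 | Do they enter the target sum? | No |
| 11.433 | Is their growth progression of existing non-target disease? | Not as classified by 11.42 |
| 11.432 / 11.433 | New lesion? | No, present at baseline |
| 11.44 | Overall status | Target SD, no non-target progression, no new site: SD |

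Under 16.21 this patient is a success. If the two lesions were non-target, the reader could consider unequivocal progression under 11.433, subject to its note. The two-node limit creates the same gap for measurable lymph nodes.

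**Step 2: reproduce the plan's operating characteristics.** Inputs from 16.21 and 16.22: 14 patients in stage 1, continue with 8 or more successes; 30 in total, positive with 19 or more; null 0.50, alternative 0.70. With success probability p,

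P(positive) = Σ over x = 8 to 14 of P[Bin(14, p) = x] × P[Bin(16, p) ≥ 19 − x].

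| p | Computed | Table in 16.22 |
|---|---|---|
| 0.50 | 0.0900 | 0.091 |
| 0.55 | 0.2116 | 0.210 |
| 0.60 | 0.3981 | 0.398 |
| 0.65 | 0.6158 | 0.613 |
| 0.70 | 0.8065 | 0.806 |

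Agreement is within 0.003. The small differences do not bear on this point.

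**Step 3: illustrate the consequence.** Let m be the share of true failures at the first scan that are scored as successes because the growth lies only in unclassified lesions. The documents give no value for m; it is an assumption. At a true success rate of 0.50 the apparent rate is 0.50 + 0.50m, and the expected number of misclassified patients among 30 is 30 × 0.50m.

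| m (assumed) | Apparent rate | Misclassified, of 30 | P(positive) |
|---|---|---|---|
| 0 | 0.500 | 0 | 0.090 |
| 2% | 0.510 | 0.3 | 0.109 |
| 5% | 0.525 | 0.75 | 0.142 |
| 10% | 0.550 | 1.5 | 0.212 |

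**Step 4: check the response endpoints.** Complete response on non-target disease requires "Disappearance of all non-target lesions", so a persisting surplus lesion does not block it. If that lesion were non-target and persisted, 11.44 would give PR instead of CR. Section 16.33 counts CR or PR, and 16.34 starts duration of response at CR or PR, so neither the response rate nor the start of duration changes. Only missed progression matters, through the end date.

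**The case against.** The strongest counter-argument is that RECIST v1.1 governs. Sections 11.0, 16.21, 16.32 and 16.33 all cite it, 11.42 does not contain the word only, and the 11.44 table appears to assume that target, non-target and new disease cover everything. Sites trained in the guideline may already follow surplus lesions as non-target. This limits the practical effect but does not close the gap. Section 11.0 says the study uses its own RECIST template, 11.44 ties that template to data collection and analysis, and the template has no rule for these lesions. If some sites follow the guideline and others follow 11.42, scoring differs between sites.

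Four further objections stand and narrow the point:

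- In the four-lesion example, a reader might infer that reclassification would make progression certain. The note in 11.433 makes it a judgement and warns against letting non-target growth normally override target status.
- A reader might infer that the gap inflates the response rate. It does not, because CR and PR count alike.
- Targets are chosen by size and to represent all involved sites, new lesions still count, and symptomatic deterioration (11.45) can still give progression on clinical grounds. Progression seen only in surplus lesions may be infrequent.
- The baseline RECIST form is listed in 18.1 but not reproduced. The text does not require these lesions to be recorded; whether the form captures them cannot be determined.

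**Conclusion.** The gap in the text is real. Measurable lesions and nodes beyond the 11.41 limits fall in no class, and their growth, followed as written, triggers none of the progression rules. Any resulting error favours success at the first scan and lengthens PFS and duration of response. Inconsistent scoring between sites is a second risk.

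The size is unknown. The probabilities 0.109, 0.142 and 0.212 are the design's own power curve read at assumed apparent rates of 51%, 52.5% and 55%. A reader might take them as the trial's actual false-positive rate; the documents do not support that, because they give no frequency for surplus lesions or for progression confined to them. Nor do they show that the primary result is biased in fact, since sites may already apply the guideline. What the figures do show is that, with 30 patients, about one misclassified patient is enough to matter: 0.75 expected misclassifications take the false-positive chance from 0.090 to 0.142. The conclusion about the wording depends on none of these figures. The correction should be made because it is cheap and the primary endpoint depends on the rule.

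**What to change.** Reword 11.42 so that all disease present at baseline and not selected as a target lesion or target lymph node is non-target. This covers non-measurable disease under 11.22 and measurable lesions and nodes beyond the limits in 11.41. State that it is recorded at baseline and followed under 11.433, including the note that unequivocal progression must represent a change in overall disease status. Align the instruction on the baseline RECIST form, and re-check the existing scans of any patients already assessed.

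The cost is one reworded sentence, a form instruction and slightly more recording. The scheduled CT or MRI already covers chest, abdomen and pelvis, so no extra imaging is needed, and the sample size and decision rule are unchanged. The observed success rate may be slightly lower.

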11.43 Response Criteria

- 11.431 All target lesions and target lymph nodes followed by CT/MRI must be measured on re-evaluation at evaluation times specified in Section 11.1. Specifically, a change in objective status to either a PR or CR cannot be done without re-measuring target lesions and target lymph nodes.

Note: Non-target lesions and non-target lymph nodes should be evaluated at each assessment, especially in the case of first response or confirmation of response. In selected circumstances, certain non-target organs may be evaluated less frequently. For example, bone scans may need to be repeated only when complete response is identified in target disease or when progression in bone is suspected.

11.432 Evaluation of Target Lesions

- Complete Response (CR): All of the following must be true:
 - a. Disappearance of all target lesions.
 - b. Each target lymph node must have reduction in short axis to <1.0 cm.
- Partial Response (PR): At least a 30% decrease in PBSD (sum of the longest diameter for all target lesions plus the sum of the short axis of all the target lymph nodes at current evaluation) taking as reference the BSD (*see* Section 11.41).
- Progression (PD): At least one of the following must be true:
 - a. At least one new malignant lesion, which also includes any lymph node that was normal at baseline (< 1.0 cm short axis) and increased to ≥ 1.0 cm short axis during follow-up.
 - b. At least a 20% increase in PBSD (sum of the longest diameter for all target lesions plus the sum of the short axis of all the target lymph nodes at current evaluation) taking as reference the MSD (Section 11.41). In addition, the PBSD must also demonstrate an absolute increase of at least 0.5 cm from the MSD.
- Stable Disease (SD): Neither sufficient shrinkage to qualify for PR, nor sufficient increase to qualify for PD taking as reference the MSD.

11.433 Evaluation of Non-Target Lesions & Non-target Lymph Nodes

- Complete Response (CR): All of the following must be true:
 - a. Disappearance of all non-target lesions.
 - b. Each non-target lymph node must have a reduction in short axis to <1.0 cm.
- Non-CR/Non-PD: Persistence of one or more non-target lesions or non-target lymph nodes.
- Progression (PD): At least one of the following must be true:
 - a. At least one new malignant lesion, which also includes any lymph node that was normal at baseline (< 1.0 cm short axis) and increased to ≥ 1.0 cm short axis during follow-up.
 - b. Unequivocal progression of existing non-target lesions and non-target lymph nodes. (NOTE: Unequivocal progression should not normally trump target lesion and target lymph node status. It must be representative of overall disease status change.)

11.44 Overall Objective Status

The overall objective status for an evaluation is determined by combining the patient's status on target lesions, target lymph nodes, non-target lesions, non-target lymph nodes, and new disease as defined in the following tables:

For Patients with Measurable Disease

Target Lesions & Target Lymph Nodes	Non-Target Lesions & Non-Target Lymph Nodes	New Sites of Disease	Overall Objective Status
CR	CR	No	CR
CR	Non-CR/Non-PD	No	PR
PR	CR Non-CR/Non-PD	No	PR
CR/PR	Not All Evaluated*	No	PR**
SD	CR Non-CR/Non-PD Not All Evaluated*	No	SD
Not all Evaluated	CR Non-CR/Non-PD Not All Evaluated*	No	Not Evaluated (NE)
PD	Unequivocal PD CR Non-CR/Non-PD Not All Evaluated*	Yes or No	PD
CR/PR/SD/PD/Not all Evaluated	Unequivocal PD	Yes or No	PD
CR/PR/SD/PD/Not all Evaluated	CR Non-CR/Non-PD Not All Evaluated*	Yes	PD

*See Section 11.431

** NOTE: This study uses the protocol RECIST v1.1 template dated 2/16/2011. For data collection and analysis purposes the objective status changed from SD to PR in the ACCRU protocol RECIST v1.1 template as of 2/16/2011 and to match RECIST v1.1 requirements.

For Patients with Non-Measurable Disease Only:

Non-Target Lesions & Non-Target Lymph Nodes	New Sites of Disease	Overall Objective Status
CR	No	CR
Non-CR/Non-PD	No	Non-CR/Non-PD
Not All Evaluated*	No	Not Evaluated (NE)
Unequivocal PD	Yes or No	PD
Any	Yes	PD

*See Section 11.431

- 11.45 Symptomatic Deterioration: Patients with global deterioration of health status requiring discontinuation of treatment without objective evidence of disease progression at that time, and not either related to study treatment or other medical conditions, should be reported as PD due to “symptomatic deterioration.” Every effort should be made to document the objective progression even after discontinuation of treatment due to symptomatic deterioration. A patient is classified as having PD due to “symptomatic deterioration” if any of the following occur that are not either related to study treatment or other medical conditions:
- Weight loss >10% of body weight.
 - Worsening of tumor-related symptoms.
 - Decline in performance status of >1 level on ECOG scale.

